## 2.5 Intervention and control

### 2.5.1 Control wedges

All sites start as control sites for 6 months. After the first 6 months, hospitals will cross over to the intervention at 6-monthly intervals (see Figure 1). During control wedges, sites will provide patients with treatment as usual according to the routine practice of each hospital, and in accordance with the practice of the healthcare system in each country.

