### 2.5.2 Intervention wedges

During intervention wedges, the hospital sites will provide the ICLEAR-EU intervention. The developed Intervention Manual (Version 5, Post Pilot Clinical Manual; see Deliverable D2.6) contains the full intervention description, which will be provided for the clinicians delivering the intervention at the hospital sites.

The intervention consists of five core components supported by two implementation strategies, shown in Figure 3.

[figure not shown]

Figure 3. Overview of the ICLEAR-EU intervention

The five core components are:

1. **Identification** of unmet palliative care needs using assessment tools
2. **Communication** about goals of care and sharing with patient, family, and care team.
3. Shared decision-making regarding **Levels of Escalation**, contributing to a patient management plan for future care
4. Initiating **advance care planning** conversations with the patient and family (if present)
5. Ongoing **Review** and management of palliative care needs during follow-up visits with healthcare professionals, and revision of the patient management plan if or when necessary.

The implementation strategies consist of **training** for clinicians delivering the intervention, and overall **integration of palliative care** by improving inter- and multidisciplinary communication via shared reporting and outreach from hospital to community care. To achieve this, a weekly multidisciplinary ICLEAR-EU meeting will be implemented where the patients will be presented to discuss goals of care, levels of escalation and potential treatment plans. A form will be used to summarize the use of the intervention for each participant (the ICLEAR-EU form). The intervention is provided at the service level in each hospital. When hospitals are in the intervention wedge, they will apply the patient flow and deliver core components to patients with advanced COPD who are admitted for an exacerbation, as shown in Figure 4.

[figure not shown]

Figure 4. Diagram of pre-intervention steps and intervention procedures for hospitals in intervention condition

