### 2.6.3 Secondary outcomes

Secondary outcomes measured during the study are shown in Table 2 below, along with the timing for data collection.

Table 2. Constructs measured in the study, corresponding instruments, scheduling

Construct	Data collection measure	Completed by	Timing		
			T0 (Baseline)	T1 (30 days post-baseline)	T2 (90 days post-baseline)
Patient outcomes					
Demographics	

- Age

- Sex

- Marital status

- Children

- Cohabitation status

- Hours of transit to hospital where recent hospitalization occurred

- Highest level of education completed

- Employment status

- Comfort of living on household income

- Financial difficulties due to physical condition or treatment

- Country of birth + parent country of birth (if different from respondent birth country)

	Patient	x		
Perception of illness	Brief Illness Perception Questionnaire 	Patient	x	x	x

Quality of life	SF-CRQ   EQ-5D-5L   ICECAP-SCM 	Patient	x	x	x
Mental wellbeing	PHQ-4 	Patient	x	x	x
Existential wellbeing	MQOL-R existential subscale 	Patient	x	x	x
Preferred place of death + whether this has been discussed with health care professionals	Questionnaire item	Patient	x	x	x
Presence of advance decisions to refuse treatment (ADRTs) and advance care plans (ACPs)	ICLEAR-EU form and medical notes	Physician/researcher			x
[Bereaved] caregiver outcomes					
Demographics	
 
- Age
 
- Sex
 
- Marital status
 
- Children
 
- Cohabitation status
 
- Relationship to the person with COPD
 
- Living with the person with COPD
 
- Distance from home of person with COPD (hours)
 
- Highest level of education completed
 
- Employment status
 
- Comfort of living on household income
 
- Financial difficulties due to physical condition or treatment of family member with COPD
 
- Country of birth + parent country of birth (if different from respondent birth country)
 
	Caregiver	x		

Quality of Life	EQ-5D-5L 	Caregiver	x	x	x
Mental wellbeing	PHQ-4 	Caregiver	x	x	x
Existential wellbeing	MQOL-R existential subscale 	Caregiver	x	x	x
Family carer burden	ZBI-12 	Caregiver	x	x	x

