Bereaved caregiver views of quality of care and death	VOICES-SF 	Bereaved caregiver	3 months post-bereavement		
Healthcare utilisation of enrolled patients					
Place of death	Medical notes or phone GP	Researcher	As appropriate		
Concordance between preferred place of death and actual place of death	Questionnaire item Medical notes or phone GP	Researcher	As appropriate		
All-cause mortality	Medical notes	Physician/researcher	As appropriate		
Number of readmissions to hospital	Medical notes	Physician/researcher			x
Median length of hospital stays on readmission	Medical notes	Physician/researcher			x
Number of referrals to specialist palliative care	ICLEAR-EU form and medical notes	Physician/researcher			x
Intensive Care Unit (ICU) admissions	Medical notes	Physician/researcher			x
Emergency Department admissions	Medical notes	Physician/researcher			x

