### 2.6.5.1 PRISM/RE-AIM

We will use the PRISM/RE-AIM framework to evaluate the Reach, Effectiveness, Adoption, Implementation, and Maintenance domains of the intervention alongside key contextual factors. These will be qualitatively and quantitatively assessed as shown in Table 3.

Table 3. RE-AIM outcomes and measures

	Outcome	Measure	Timing of measurement	Completed by
Reach	Training attendance	Training attendance list: 

- Attendance numbers

- Professions represented

	After each ICLEAR-EU training	Coordinator/ data collector
	ICLEAR-EU Meeting attendance	ICLEAR-EU meeting attendance list: 

- Attendance numbers

- Professions represented

	After each ICLEAR-EU meeting	Coordinator/ data collector
	Total number of patients included vs.not included in study	

- Admitted for acute exacerbation

- Screened for study

- Included in study

	After every wedge	Coordinator/ data collector
Effectiveness	Effectiveness of training	Self-Efficacy regarding end-of-life communication (S-EOLC)   Palliative and end-of-life care-specific education needs (End-of-life Professional Caregiver Survey (EPCS)) 	Pre: 1-4 weeks before training  Post: 1-4 weeks after start first intervention wedge	ICLEAR-EU team members
	Experiences with ICLEAR-EU	Interview with patients, (bereaved) relatives, and clinicians	Patients: Approx. 4 weeks after hospital discharge  Bereaved relatives: 3 months after bereavement	Local research team

			Clinicians: During follow-up period after last wedge	
Adoption	ICLEAR-EU meeting	Addendum ICLEAR-EU meeting form -How often? -Duration? -How many patients discussed? -How many patients not discussed? Why not?	After each ICLEAR-EU meeting	Coordinator
Implementation	Adherence	-Number of inclusions (calculated from inclusion log) -Fidelity checklist	After every wedge	Coordinator
	Ease of use	Interval scale	After every wedge	ICLEAR-EU team members
	Satisfaction with ICLEAR-EU training/trainer	Evaluation questionnaire	Immediately after training	ICLEAR-EU team members
	Satisfaction with the ICLEAR-EU intervention	Interval scale	After every wedge	ICLEAR-EU team members
	Fidelity	Core components ICLEAR-EU per patient: check based on ICLEAR-EU form or medical record	After every wedge	ICLEAR-EU coordinator for every patient

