## 2.10 Data collection procedures

The **primary outcome** (percentage of participating patients readmitted to hospital within 90 days of baseline, or until death if within these 90 days) will be collected via routinely-collected data regarding hospitalization in the patient (electronic) medical record. A data retrieval form will be used to collect data from the patient health record.

Patients and family caregivers enrolled in the study will be asked to complete questionnaires for **secondary outcomes** at baseline (T0, immediately following informed consent), and at 30 and 90 days post-baseline. If a patient dies during the trial, caregivers who consented will be contacted 3 months post-bereavement to complete the VOICES-SF questionnaire. Additional data regarding healthcare utilisation of enrolled patients will be collected through medical notes, consulting the patient's ICLEAR-EU form, and consulting with the general practitioner (GP) or other home/community care when possible and appropriate.

Data for the **cost-effectiveness evaluation** includes the CSRI and EuroQol (EQ-5D-5L) at 30 and 90 days, alongside other trial data collection through the participant interview. Unit costs will be identified first by literature search and, where necessary, by calculation by the research team. The economic evaluation will also utilize the hospital data to model intensity of hospital stay for a given patient profile.

For the **process evaluation**, both quantitative and qualitative data addressing the PRISM/RE-AIM domains will be collected throughout the study (see Table 3 for timing). Quantitative data will be collected using structured checklists, questionnaires, monitoring recruitment numbers, and short surveys; these will be conducted at set time points at the trial timeline and intervention timeline level, including pre-and post-training, after ICLEAR-EU meetings, and at the end of a wedge. Data will be collected via ICLEAR-EU team members attending the trainings and ICLEAR-EU meetings, and from the coordinator and/or clinical champion.

Semi-structured interviews for qualitative data collection will be conducted as follows:

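### Two secondary outcomes (advance decisions/care plans and specialist palliative referrals) have one more data source in intervention wedges than in control wedges, so detection can differ in the intervention's favour

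*Protocol*

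**What the plan says.** Protocol section 2.6.3, Table 2, lists the same double source, "ICLEAR-EU form and medical notes", for two rows at the 90-day assessment: advance decisions and advance care plans, and "Number of referrals to specialist palliative care". The neighbouring rows taken from the record (mortality, readmissions, length of stay, ICU and emergency admissions) name medical notes only.

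Section 2.10 repeats the form as a source for healthcare-utilisation data, beside medical notes: "consulting the patient's ICLEAR-EU form, and consulting with the general practitioner (GP") or other community care where possible. It neither limits this by condition nor names a control counterpart to the form.

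The form is introduced in section 2.5.2, on intervention wedges: "A form will be used to summarize the use of the intervention for each participant (the ICLEAR-EU form"). That section opens with "During intervention wedges, the hospital sites will provide the ICLEAR-EU intervention". Section 2.5.1 says of the other condition: "During control wedges, sites will provide patients with treatment as usual according to the routine practice of each hospital", and mentions no form. In Table 3 (section 2.6.5.1) the form is also a fidelity source: "Core components ICLEAR-EU per patient: check based on ICLEAR-EU form or medical record".

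**The concern.** Both outcomes are compared between conditions, with models similar to the primary one (section 2.12.2). If one condition has an additional place in which an event can be found, recorded rates can differ although care does not. The analysis cannot separate the two, because the change of source coincides with the change of condition; neither the randomised crossover time nor the fixed effects for time and country help. Extraction is by a physician or researcher, and section 2.9.1 accepts that researchers cannot be fully blinded.

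The direction matters. Advance care planning is one of the five core components, and the Introduction presents limited access to palliative care as the problem to be solved. More recorded plans and referrals would be read as success. For care plans, a document that shows delivery of the intervention could also count as evidence of its effect.

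**Working it through.** **Step 1: sources by condition, from the text.**

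| Outcome | Control wedge | Intervention wedge |
|---|---|---|
| Advance decisions / care plans | Medical notes | Medical notes + ICLEAR-EU form |
| Specialist palliative referrals | Medical notes; GP/community contact (2.10) | Medical notes; GP/community contact (2.10) + ICLEAR-EU form |

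No sentence says that control patients lack the form. It follows from 2.5.1 and 2.5.2: a form that summarises use of an intervention has nothing to summarise for a patient who did not receive it.

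**Step 2: size with no true effect.** The protocol gives no figure to reproduce: no rate for either outcome and no completeness of notes. All inputs here are assumptions. Let *p* be the true rate in both conditions, *s* the share of true cases found in the sources common to both conditions, and *f* the share of missed cases that the form recovers.

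- Control, recorded: *p·s*
- Intervention, recorded: *p·[s + (1 − s)·f]*
- False gain: *p·(1 − s)·f*, which is never negative

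With *p* = 0.40:

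| *s* | Control | Intervention, *f* = 1 | Gain | Intervention, *f* = 0.5 | Gain |
|---|---|---|---|---|---|
| 0.70 | 28% | 40% | 12 points | 34% | 6 points |
| 0.90 | 36% | 40% | 4 points | 38% | 2 points |
| 0.95 | 38% | 40% | 2 points | 39% | 1 point |

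At lower rates the gain shrinks. With *p* = 0.20, *s* = 0.80, *f* = 0.50 the recorded rates are 16% and 18%, odds ratio (0.18/0.82)/(0.16/0.84) = 1.15. With *p* = 0.10, *s* = 0.95, *f* = 0.25 the gain is 0.1 point.

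**Step 3: effect on the test.** This uses the Hussey–Hughes variance for the planned layout: *I* = 18 hospitals, *T* = 4 wedges, 6 hospitals per crossover time, giving *U* = 36, *W* = 504, *V* = 84. The ICC of 0.05 is stated for the primary outcome and borrowed here. Evaluable patients per hospital and wedge are 17 × 0.7 = 11.9 after the stated 30% drop-out. Outcomes are treated as binary (for referrals: any referral), without the condition-by-time interaction.

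For 16% against 18%:
- total variance 0.17 × 0.83 = 0.1411
- τ² = 0.05 × 0.1411 = 0.00706
- σ² = 0.95 × 0.1411 / 11.9 = 0.01126
- Var = *I*σ²(σ² + *T*τ²) / [(*IU* − *W*)σ² + (*U*² + *ITU* − *TW* − *IV*)τ²] = 18 × 0.01126 × 0.03948 / (144 × 0.01126 + 360 × 0.00706) = 0.00192, so SE = 0.0439
- chance of a significant result favouring the intervention: Φ(0.02/0.0439 − 1.96) = 6.6%, against a nominal 2.5% (7.7% with all 17 evaluable)

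Over *p* = 0.10–0.40, *s* = 0.60–0.95 and *f* = 0.25–0.90, the odds ratio runs from 1.01 to 1.97 and this chance from 2.7% to 76% at 11.9 evaluable patients (up to 88% at 17).

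**Step 4: with common sources.** The form adds nothing (*f* = 0), the false gain is zero, and the upper-tail error returns to 2.5%.

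**The case against.** The strongest reply has four parts.

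*The form is an addition, not the measurement.* A reader might infer that these outcomes are read from the form and that controls go unmeasured, or that control events come from notes alone. The protocol supports neither. Both rows name medical notes, which exist in both conditions, and section 2.10 allows GP or community contact for utilisation data, hence for referrals, in either condition. This stands: the defect is one extra source.

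*The form's content is unknown.* Its fields are not in the protocol, and nothing says whether the completed form is filed in the medical record. A reader might take it for a structured record of goals, escalation and plans; section 2.5.2 says only that it summarises intervention use. This limits any claim about size. Filing the form in the record would not cure the asymmetry, because the extra source would then sit inside the notes.

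*Documentation is partly the effect sought.* Section 1.1 words the outcome as the documentation of advance care planning, and initiating such planning is a core component. Some form-only entries may therefore be genuine effect, and banning them outright could bias towards no difference. This stands, and it argues for keeping them in a sensitivity analysis.

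*The bias may be negligible.* It needs notes that are incomplete and a form that adds cases not found elsewhere. A specialist referral may well leave its own trace in the notes. This also stands.

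**Conclusion.** The point holds in a limited form. As written, the plan gives intervention patients one more source than control patients for two secondary outcomes, and any resulting difference in detection favours the intervention. This rests on the firm, though unstated, inference that control patients have no ICLEAR-EU form, and on more recorded plans and referrals being read as better.

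The size is not known. Under the assumed 40% true rate, the false gain is 4–12 points at full recovery, 2–6 at half recovery, and near zero if notes are nearly complete. It would go too far to say that recorded rates will be higher in intervention wedges; they can be.

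The primary outcome comes from routine hospital records in both conditions and is not affected. The matter should be settled before extraction starts, because the data source is fixed in the protocol's own measurement table and collection section.

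**What to change.** For the main between-condition analysis, ascertain both outcomes in both conditions from the same sources: the medical record, plus GP or community contact under the same rule wherever it is used. Apply the same data retrieval form (section 2.10 already provides one for the primary outcome) and the same 90-day window. State that an ICLEAR-EU form filed in the record does not count as a source on its own in this analysis. Record the source of each event so that both analyses can be run. Keep the form for fidelity, and report form-plus-notes as a labelled sensitivity analysis; the gap between the two results shows how much rests on the extra source.

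This changes two rows of Table 2 and the matching sentence in 2.10, and uses records the plan already consults. Two costs should be stated openly. Genuine events recorded only on the form leave the main analysis, and these may be more than a few: if notes capture 70%, up to 30% of true events are at stake. The change also does not remove any effect of better note-keeping in intervention wedges.

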## 2.6.4 Health economic evaluation

We will use hospital data to quantify length and intensity of inpatient hospital stays. We will collect additional formal healthcare utilisation and unpaid family care using an adapted Client Service Receipt Inventory (CSRI), and estimate costs by combining reported frequencies with nation-specific unit costs. We will collect health-related quality of life using EuroQoL EQ-5D-5L, converting responses to quality-adjusted life years (QALYs) using nation-specific population preference weights and mortality data from the main trial.

## 2.6.5 Process evaluation

During this trial, we will conduct an embedded process evaluation in all sites. The full protocol for the Process and Implementation Evaluation can be found in the Project Deliverable D8.1.

To better understand current practices in the hospitals involved in the trial, which provide the context in which the trial is conducted and the intervention implemented, we will administer a questionnaire about current care practices at the end of each wedge, to be completed by the ICLEAR-EU coordinator or clinical champion.

Additionally, to assess current practices as they relate specifically to the ICLEAR-EU intervention model, we will also conduct a one-time interview in each hospital with the ICLEAR-EU coordinator or clinical champion. The interview will be conducted during the transition phase, prior to the intervention training.

### 2.6.5.1 PRISM/RE-AIM

We will use the PRISM/RE-AIM framework to evaluate the Reach, Effectiveness, Adoption, Implementation, and Maintenance domains of the intervention alongside key contextual factors. These will be qualitatively and quantitatively assessed as shown in Table 3.

Table 3. RE-AIM outcomes and measures

	Outcome	Measure	Timing of measurement	Completed by
Reach	Training attendance	Training attendance list: 

- Attendance numbers

- Professions represented

	After each ICLEAR-EU training	Coordinator/ data collector
	ICLEAR-EU Meeting attendance	ICLEAR-EU meeting attendance list: 

- Attendance numbers

- Professions represented

	After each ICLEAR-EU meeting	Coordinator/ data collector
	Total number of patients included vs.not included in study	

- Admitted for acute exacerbation

- Screened for study

- Included in study

	After every wedge	Coordinator/ data collector
Effectiveness	Effectiveness of training	Self-Efficacy regarding end-of-life communication (S-EOLC)   Palliative and end-of-life care-specific education needs (End-of-life Professional Caregiver Survey (EPCS)) 	Pre: 1-4 weeks before training  Post: 1-4 weeks after start first intervention wedge	ICLEAR-EU team members
	Experiences with ICLEAR-EU	Interview with patients, (bereaved) relatives, and clinicians	Patients: Approx. 4 weeks after hospital discharge  Bereaved relatives: 3 months after bereavement	Local research team

			Clinicians: During follow-up period after last wedge	
Adoption	ICLEAR-EU meeting	Addendum ICLEAR-EU meeting form -How often? -Duration? -How many patients discussed? -How many patients not discussed? Why not?	After each ICLEAR-EU meeting	Coordinator
Implementation	Adherence	-Number of inclusions (calculated from inclusion log) -Fidelity checklist	After every wedge	Coordinator
	Ease of use	Interval scale	After every wedge	ICLEAR-EU team members
	Satisfaction with ICLEAR-EU training/trainer	Evaluation questionnaire	Immediately after training	ICLEAR-EU team members
	Satisfaction with the ICLEAR-EU intervention	Interval scale	After every wedge	ICLEAR-EU team members
	Fidelity	Core components ICLEAR-EU per patient: check based on ICLEAR-EU form or medical record	After every wedge	ICLEAR-EU coordinator for every patient
	Barriers and facilitators to implementation	Short questionnaire with text box  Regular check-in with local research team by phone	After every intervention wedge	Local research team and coordinator
Maintenance	Intention for using ICLEAR-EU in the future	Interval scale	After last wedge	ICLEAR-EU team members, e.g. clinical champion and coordinator
	Organizational intention for long-	Interval scale	After last wedge	ICLEAR-EU team members, e.g.

	term implementation			clinical champion and coordinator
	Experiences with and recommendations for improving usability of intervention program	Interview with two clinicians from the ICLEAR-EU team	After last wedge	ICLEAR-EU team members, e.g. clinical champion and coordinator

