From the UK-based intervention, the consortium adapted the intervention through consultation meetings with clinicians and patients/patient representatives in six countries (Belgium, the Netherlands, the United Kingdom, Denmark, Hungary, and Portugal), then pilot-tested the intervention internationally.

The present protocol concerns the large-scale international trial of the adapted and pilot-tested ICLEAR-EU intervention. In this study, patients with advanced COPD who are admitted to the hospital for more than 48 hours due to an acute exacerbation of their COPD, are invited to participate and will be followed up for 90 days.

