## **2 Methods**

### **2.1 Trial design**

We have chosen a stepped wedge cluster-randomized controlled trial design for this study, which is a pragmatic design that allows every participating hospital the opportunity to receive the intervention.

The stepped wedge cluster-randomized controlled trial will proceed in a similar fashion across the six countries (Belgium, the Netherlands, the United Kingdom, Denmark, Hungary, and Portugal). Clustering is at the level of hospital sites. Each country will include three hospitals. A schematic representation of the trial design is shown in Figure 1.

[figure not shown]

Figure 1. Stepped wedge design of the trial

Each hospital will go through four wedges, each wedge with a duration of six months, for a total of 24 months. Each hospital starts in control condition and crosses over to the intervention condition at 6, 12 or 18 months. The timing of cross-over will be randomly assigned at study onset. Before a hospital crosses over from the control condition to the intervention condition, a 30-day transition period will be integrated into the last control wedge, during which clinicians will receive the intervention training and implementation support will be provided.

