## 2.3 Eligibility criteria

**Hospitals:** Hospitals that typically admit 100–500 patients annually for COPD-related causes and indicate a willingness to implement ICLEAR-EU meetings will be included in the study. Hospital sites have in-patient respiratory beds.

**Patients and family caregivers:** Patients with advanced COPD living at home, who are admitted to the hospital for more than 48 hours because of an acute exacerbation of COPD and who will potentially benefit from an integrated palliative care approach, are eligible for participation. For data collection purposes, patients who are enrolled during a control wedge will not be re-enrolled for data collection in the intervention wedge.

Patients may also indicate a family caregiver for participation. We consider the family caregiver to be “any relative, friend, or partner who has a significant relationship and provides assistance (physical, social, and/or psychological)” to the patient. Not including a family caregiver does not exclude the patient from eligibility.

Inclusion and exclusion criteria for patients and family caregivers are described in Table 1.

Table 1. Patient and family caregiver inclusion and exclusion criteria

Patient	Family Caregiver
Inclusion criteria	

 
Have a diagnosis of advanced COPD*
 
Admission to the respiratory ward of the hospital that lasts <math>\geq</math> 48 hours (or likely to be admitted for <math>\geq</math> 48 hours) for an acute exacerbation
 
Live at home
 
	
 
Identified by the patient as the person who gives him or her the most help and support at home on a regular basis
 
Age 18 years or over
 

Exclusion criteria	

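### The per-patient fidelity check is tied to the end of the wedge, so ongoing review (core component 5) is scored over unequal and, for about half the patients, truncated follow-up

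*Protocol*

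**What the plan says.** Table 3 in Protocol section 2.6.5.1 lists, under Implementation, a Fidelity outcome measured as "Core components ICLEAR-EU per patient: check based on ICLEAR-EU form or medical record". The ICLEAR-EU coordinator completes it for every patient, and its timing is "After every wedge". The Adherence row has the same timing and lists two items: "Number of inclusions (calculated from inclusion log") and a fidelity checklist. Section 2.10 says that quantitative process data are collected at set time points, "including pre-and post-training, after ICLEAR-EU meetings, and at the end of a wedge", and refers to Table 3 for timing.

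Section 2.5.2 defines five core components. The fifth is continuing review and "management of palliative care needs during follow-up visits with healthcare professionals", with the management plan revised when needed. No time window or number of reviews is given.

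On the calendar, section 2.1 states: "Each hospital will go through four wedges, each wedge with a duration of six months, for a total of 24 months". The Introduction says that eligible patients "are invited to participate and will be followed up for 90 days".

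**The concern.** Fidelity is a patient-level measure, but its timing is set by the hospital's calendar. Patients enter throughout a six-month wedge. At wedge close, one enrolled in the first week has had nearly six months in which a review could be recorded, and one enrolled in the last week has had a few days. Component 5 is the only component defined by what happens at later visits, so it is the one whose score clearly depends on elapsed time.

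The stake lies in objective 1f (section 1.1), which promises to evaluate feasibility, barriers and facilitators, and the mechanisms behind the outcomes. If reviews that take place after the check are never counted, ongoing review looks less well delivered than it was. Patients with early and late enrolment dates are also not comparable on it. Either effect could mislead the reading of a null or positive trial result.

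**Working it through.** The protocol gives no figure of its own for this point. The inputs are:

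- Wedge length: six months, taken as 182.5 days (section 2.1).
- Patient follow-up: 90 days (Introduction; T2 in Table 2).
- Recruitment: on average 17 patients per hospital per wedge (section 2.7). Check: 18 hospitals × 4 wedges × 17 = 1224, the stated total.
- Crossover at 6, 12 or 18 months, one hospital per country at each step (sections 2.1 and 2.9). A hospital therefore has 3, 2 or 1 intervention wedges.
- Assumption: even accrual within a wedge. The protocol gives only the average per wedge.

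**Patients short of day 90 when the wedge closes.** These are the patients enrolled in its last 90 days.

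- Share = follow-up / wedge length = 90/182.5 = 49.3% (50.0% with a 180-day wedge).
- Per hospital-wedge: 17 × 0.493 = 8.4 patients.
- Intervention hospital-wedges: 6 × (3 + 2 + 1) = 36. Planned intervention patients: 36 × 17 = 612.
- Affected: 612 × 0.493 = about 302.
- Patients short of day 30: 30/182.5 = 16.4%, or 2.8 of 17.

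**If the check is made some days after wedge close.** With a lag of L days, for L up to 90, the share is (90 − L)/182.5.

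| Lag L (days) | Share short of day 90 | Of 612 |
|---|---|---|
| 0 | 49.3% | about 302 |
| 30 | 60/182.5 = 32.9% | about 201 |
| 60 | 30/182.5 = 16.4% | about 101 |
| 90 | 0% | 0 |

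**If earlier patients are re-checked at each later wedge.** The protocol does not state this, but under it only the last wedge stays truncated, because no wedge check follows.

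- Affected: 18 × 17 × 0.493 = about 151, and 151/612 = 25%.
- By randomised sequence, the share of a hospital's intervention patients is 8.4/51 = 16% with three intervention wedges, 8.4/34 = 25% with two and 8.4/17 = 49% with one. Apparent fidelity would then vary with crossover time.

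**The case against.** The strongest reply is that the timing wording is loose and not wrong. "After every wedge" need not mean closing day. The list in section 2.10 is general, the medical record stays available for a later look, and section 2.6.5 places the full process-evaluation protocol in Deliverable D8.1, which is not at hand and may set a window. No scoring rule is given, so nothing says that a patient without a recorded review is marked as not delivered. Ninety days is the outcome follow-up and not a stated delivery period for component 5.

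Much of this stands, and it limits the claim. The 49% is the share with less than 90 days of observation. It is not a share mis-scored. But the reply does not remove the point. Neither the Fidelity row nor the text states a lag or re-check, including after the last wedge. Table 3 names the follow-up period explicitly for clinician interviews and does not do so here. The Objectives part of the Executive summary makes timing a core element for all countries, so the wording here matters whatever D8.1 adds.

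Three stronger readings are not supported:

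- **That adherence is measured only by enrolment.** The number of inclusions does measure recruitment, and Reach already counts it. But the Adherence row also lists the fidelity checklist. Patients discussed and not discussed at meetings are recorded under Adoption, and admitted and screened patients under Reach. No replacement measure is needed.
- **That 17 inclusions can be set against hospital volume to show low reach.** Section 2.3 describes "Hospitals that typically admit 100–500 patients annually for COPD-related causes". Those are all COPD-related admissions and not patients meeting Table 1, so the ratio says nothing about adherence.
- **That delivered exposure as a whole is mis-measured, or the trial's main result biased.** Components 1 to 4 are not tied to day 90. Sections 2.12 and 2.12.1 analyse by condition at entry, with no fidelity or adherence term.

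**Conclusion.** The point holds as a correction to the process evaluation. As timed, the check gives component 5 an observation period set by enrolment date. With even accrual and a check at wedge close, about 49% of each wedge's patients have less than 90 days of observation: about 8 of 17 per hospital-wedge and about 300 of 612 planned intervention patients. A lag before the check reduces this share, and it reaches zero only at 90 days. Uneven accrual would move it either way.

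The likely direction is under-recording of ongoing review. Its size cannot be given, because the protocol states neither when reviews are due nor how they are scored. Sample size, power and the primary intention-to-treat comparison are untouched.

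**What to change.** In Table 3, change the timing of the Fidelity row, and of the fidelity checklist in the Adherence row, from after every wedge to each patient's T2 (90 days, or death if earlier). Bring the end-of-wedge wording in section 2.10 into line. Component 5 is then read over the same period for every patient who survives to T2. This fixes an observation window for measurement and does not set when reviews should take place.

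The check can be combined with the T2 review of the ICLEAR-EU form and medical notes that Table 2 already schedules for advance care planning and specialist palliative care referrals. No new visit or data source is needed. Table 2 assigns that review to a physician or researcher, while Table 3 assigns fidelity to the coordinator, so who completes it must be agreed. For last-wedge patients the records must be read up to 90 days after the wedge closes in any case, for the primary outcome.

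The cost is delay: complete fidelity data for a wedge arrive about three months later. An interim count at wedge end can still be fed back to sites if it is labelled as incomplete for component 5.
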